2.3.4.1 CURRENT CLINICAL EXPERIENCE

The ChEVAS procedure has been described in benchtop studies,^{99, 100} case reports^{94,98,101,102,103,104,105,106,107,108,109} and in small series involving mainly emergent cases.^{110,111,112} It was apparent from the early experience that standardization of the therapy with regard to technique and components was desirable.

To date there have been five articles reporting on the feasibility and safety of ChEVAS in retrospective and prospective studies of > 10 patients. The characteristics of these studies are presented in **Table 2**. The majority of patients included in these studies were male and in the eighth decade of life. A summary of the performance and safety outcomes from these studies is presented in **Table 3**.

These studies reported on primary repair or repair of a previous EVAR or aortic graft using ChEVAS. There have been other reports where ChEVAS was used, however the outcomes were not stratified by type of EVAS repair and were therefore not included in the analysis below.^{113,114} These studies, Paraskevas et al. (2018) and Youssef et al. (2017) are discussed qualitatively below.

Paraskevas et al. conducted a retrospective analysis of a prospectively maintained aneurysm database to investigate late complications following EVAR.¹¹³ There were 10 patients included in the analysis who underwent interventions for complications of the EVAR procedure. All interventions were performed using EVAS with or without chimney grafts. Technical success for Type Ia endoleaks was 100%, with no perioperative deaths. One Type Ia endoleak re-occurred during follow-up, and 2 undetermined endoleaks were explored with laparotomy were found to be Type II endoleaks.

Youssef et al. also conducted a retrospective study of patients who required reintervention following EVAR.¹¹⁴ Fifteen patients were included in the study and all patient were treated with EVAS. There were 10 patients treated with ChEVAS. Technical success was 100%, with sealing of all endoleaks. There was 1 aneurysm related death 2 months post-procedure and there was 1 renal artery injury. No other complications were observed during a mean of 8 months follow-up.

Both studies show that EVAS/ChEVAS is a beneficial treatment for failed EVAR. With good short-term results. More studies with longer follow-up are required to fully evaluate long-term outcomes.

TABLE 2: STUDY CHARACTERISTICS OF ARTICLES REPORTING ON CHEVAS FOR THE TREATMENT OF COMPLEX AAA

Publication	Subjects	Treatment Period	Mean/Median Follow-Up (months)	Mean/Median Age (years)	Male (%)	Study Design*	Country/Countries
De Bruin, J. L., J. R. Brownrigg, B. O. Patterson, A. Karthikesalingam, P. J. Holt, R. J. Hinchliffe, I. M. Loftus and M. M. Thompson. "The Endovascular Sealing Device in Combination with Parallel Grafts for Treatment of Juxta/Suprarenal Abdominal Aortic Aneurysms: Short-term Results of a Novel Alternative." Eur J Vasc Endovasc Surg 52(2016): 458-465 ¹¹⁵	28	March 2013-April 2015	4	75	79	P1SN	1 site in the U.K.
Dinkelmaier, M. K., S. P. Overeem, D. Bockler, D. E. V. JP and J. M. Heyligers. "Chimney technique in combination with a sac-anchoring endograft for juxtarenal aortic aneurysms: technical aspects and early results." J Cardiovasc Surg (Torino) 57(2016): 730-736 ¹¹⁶	16	November 2014-March 2016	1	73	87.5	P1MN	2 sites in Europe

NS, Not specified

*P, Prospective; R, Retrospective; 1, Single-Arm Study; S, Single-Center Study; M, Multi-Center Study; N, Non-Randomized Study

[†]Stenson et al. reports on the first 50 patients from the ASCEND Registry, which are included in the study by Thompson et al.

[‡]Note: the first author of this study is now the chief medical officer of Endologix.

TABLE 3: PERFORMANCE AND SAFETY OUTCOMES FOR CHEVAS IN THE TREATMENT OF COMPLEX AAA FROM THE LITERATURE

Outcome	Study				
	De Bruin et al ¹¹⁵	Dinkelmaier et al ¹¹⁶	Harrison et al ¹¹⁷	Stenson et al ^{*96}	Thompson et al ⁹⁷
Performance Outcomes					
Technical success (%)	100	100	100	100	100
Median number of chimney grafts (range)	1 (1-2)	2 (1-3)	NS	1 (1-3)	2 (1-4)
Mean procedure time (min)	185	165	NS	205	216
Mean blood loss (ml)	300	175	NS	390	339
Graft failure (%)	NS	NS	16.7	NS	NS
Migration (%)	NS	NS	NS	4.8	NS
Safety Outcomes					
30-day all-cause mortality (%)	3.6	0	11.1	3.2	2.8
All-cause mortality (%)	14.33	0	16.7	16.1	7.4
AAA-related mortality (%)	3.6	0	5.5	3.2	2.8
Stroke (%)	7.1	6.25	NS	6.5	2.6
Transient ischemic attack (%)	3.6	NS	NS	NS	NS
Type I endoleak (%)	3.6	6.25	11.1	12.9	5.8
Type II endoleak (%)	3.6	NS	NS	1.6	0
Secondary intervention (%)	14.3	18.75	NS	17.7	17.1
Limb occlusion (%)	NS	6.25	NS	3.2	NS
Graft occlusion (%)	NS	6.25	NS	3.0	NS
Chimney graft patency (%)	100	NS	NS	97	99
Dialysis (%)	NS	6.25	NS	1.6	1.3

NS, Not specified

*Stenson et al. reports on the first 50 patients from the ASCEND Registry, which are included in the study by Thompson et al.

The results presented in **Table 3** on the use of ChEVAS for the treatment of complex AAAs in general are promising. These data support a proof of concept for the use of polymer technology and EVAS with parallel grafts in managing patients with complex aortic disease. Technical success was achieved in all cases and AAA-related mortality was low ($\leq 5.5\%$). The rate of stroke was similar across studies (2.6% – 7.1%). The rate of Type I endoleaks varied from 3.6%-12.9%. A systematic review showed Type I endoleaks and chimney graft thrombosis following ChEVAR were higher than with ChEVAS, however the difference was not statistically different.⁹⁴ As to be expected, given the nature of the EVAS technique, Type II endoleaks were low across all studies. There were no Type III endoleaks reported in any of the study reviewed above.

Chimney graft patency was high across ChEVAS studies presented in **Table 3**. The majority of patients included in the studies listed in **Table 2** were treated with 1-2 chimney grafts (see **Table 3**). Stenson et al. found that with ChEVAS there were more complications where there was only a single chimney graft. They speculate that the shorter sealing zone and asymmetry of the single chimney configuration may have an effect on the columnar strength of the endograft, however the exact reasons for these complications is unknown.⁹⁶

There was one study, Thompson et al., where up to 4 chimney grafts were used.⁹⁷ They reported increased procedural blood loss in procedures with 3 or 4 chimneys, compared to procedures where there were 1 or 2 chimney grafts implanted.⁹⁷ There is evidence from ChEVAR studies that complications increase with the number of chimney grafts, which is logical, since there is a greater chance of endoleaks developing with more chimney grafts.¹¹⁸ In general, there is a lack of Nellix experience with ChEVAS with 4 chimney grafts, as only a small number of patients in the ASCEND registry were treated with 4 chimney grafts (2.6%), and there were no patients in the other studies included in **Table 3** treated with 4 chimney grafts. Due to the fact that the majority of patients can be treated with 1-3 chimney grafts and the number of complications increase with the number of chimney grafts, only 3 branches will be allowed in the IDE. In addition, ChEVAS with 4 chimney grafts is technically challenging with an increased risk of complications due to managing 4 self-expanding stents and the auxiliary vessels with increased procedure time and blood loss. At this stage, ChEVAS is not designed for complex, thoracoabdominal vessels, it is designed for the juxtrarenal/pararenal aneurysm (1-3 vessels).

There were several limitations associated with EVAS that were identified in these studies. Harrison et al. was the only EVAS study identified with longer term follow-up (4.4 years). In this study the long-term durability of EVAS was questioned, due to a high rate of graft failure > 2 years post-procedure.¹¹⁷ Therefore, frequent monitoring and imaging of patients is warranted.

Another limitation of the chimney technique is that an additional upper extremity access site is required in order to cannulate target vessels. The use of an additional upper extremity access site increases the risk of cerebral embolization when compared to fEVAR. Stroke rates of up to 10% have been reported with ChEVAR, and the incidence of stroke was higher with ChEVAR compared to open repair and fEVAR.¹¹⁵¹¹⁹¹²⁰ Therefore, methods to minimize embolizations prior, during and following the procedure are required, such as pre-operative clopidogrel and antiplatelet drugs post-operatively.⁹⁶

Despite the limitations outlined above, the results from these early experiences with ChEVAS are encouraging and show the feasibility of the technique. However, apart from the ASCEND registry, all of these studies were small and with the exception of the Harrison et al. study, lacked longer term follow-up. Therefore, larger controlled studies, with longer follow-up are required, as well as studies with comparisons to other techniques for the treatment of complex AAAs. When interpreting the results of these EVAS studies it should be noted that the majority of patients in these studies were treated prior the modifications to the

Nellix IFU in 2016. In addition, these studies report on the early experiences with the Nellix System. It is important to consider that with any new technology there is a learning curve, not only concerning the technical attributes of the device, but also concerning patient selection, and these factors may affect the long-term outcomes associated with the device. The impact of the EVAS learning curve became apparent when Endologix initiated its investigation in order to understand the mechanisms around migration, Type Ia endoleak, and aneurysm enlargement beyond the 1-year timepoint. During the development of the ChEVAS System, Endologix reviewed the ChEVAS indications based on the revised indications developed for EVAS. Specifically, an internal assessment was conducted on a subset of patients that had undergone a *de novo* ChEVAS procedure from the Global Registry and ASCEND study to confirm applicability and incorporate relevant revised anatomical criteria to the ChEVAS indications. In addition to the revised anatomical criteria captured in the narrowed indications, additional procedural techniques (e.g., proper positioning of the Nellix stents, always performing pre-fill, balloon inflation during polymer fill, confirmation of adequate seal) that were established for EVAS were also incorporated into the ChEVAS procedure. Overall, encompassing the lessons learned from these early studies, along with more careful patient selection, and standardization of the procedure should lead to improved outcomes in the future.

2.4 RISK/BENEFIT ASSESSMENT

2.4.1 RISKS

There are several risks that are specific to both the ChEVAR and ChEVAS techniques. As outlined above in **Section 2.3.4.1**, there is a risk of cerebral embolization associated with the necessity for upper extremity access to place the chimney grafts in the target vessels.^{70,119,120} The need to cross the vertebral arteries and aortic arch may also increase risk of stroke. Therefore, in order to mitigate this risk patients should be assessed for the risk of stroke and pre- and post-operative medical therapy should be considered to reduce embolizations.⁹⁶

Management of hemostasis is also a consideration with ChEVAR/ChEVAS since a higher number of chimney grafts is associated with greater procedural blood loss.⁹⁷ Furthermore, the Nellix System had higher than anticipated rates of migration and aneurysm enlargement at 2 years; however, ChEVAS is not expected to experience these events due to the revised indications for use and procedural best practices that have been incorporated to ensure optimal outcomes moving forward.¹¹⁷ Additionally, the mechanism of migration is thought to be further mitigated due to the lower force from pulsatile flow exerted on the EndoBag shelf due to the increased number of stents. When patients were treated with EVAS in accordance with the current IFU no incidences of migration were observed.¹²¹

Overall, while risks exist for the ChEVAS technique, many of these risks are comparable to those of currently available standard techniques for complex AAA. In addition, the risks associated with ChEVAS may be mitigated with careful patient selection and adherence to the current IFU for the Nellix System.

2.4.2 BENEFITS

The use of ChEVAS may offer a potential solution to the subset of patients that currently have unmet clinical needs due to being unsuitable for open surgery or need urgent treatment and cannot risk waiting for a custom fenestrated endografts. ChEVAS maintains the widespread applicability and the ability to perform this technique using off-the-shelf components in urgent and emergent cases that fEVAR lacks.

The conformability of the Nellix EndoBag filled with polymer offers a unique solution capable of sealing around the branch stent grafts to create a more durable seal with a potential reduction in risk of gutter or Type I endoleak.⁹⁴ A systematic review of ChEVAS versus ChEVAR showed a trend towards a lower rate of Type I endoleaks in patients treated with ChEVAS.⁹⁴ Additionally, chimney graft thrombosis trended lower with ChEVAS.⁹⁴ The results of the ChEVAS studies presented in **Table 3** show excellent chimney graft patency due to the improved seal of the chimney graft patency, and a low level of chimney graft occlusion.^{96,97,115,116} Better sealing and incorporation of the chimney grafts, without impacting the radial strength of the device may reduce the risk of chimney graft occlusion with ChEVAS.

The ability to completely fill the aneurysm combined with the material properties of polymer may also help stabilize the visceral segment of the aorta and reduce the occurrence rates of branch stent graft fractures. Furthermore, the polymer based ChEVAS technique may be associated with less aortic neck dilatation, since a self-expanding aortic stent is not used at the proximal seal zone. This speculation, however, must await long term anatomic outcomes.¹²²

As with EVAS, ChEVAS should offer the same unique advantages associated with the aneurysm sealing technique. Firstly, there may be a reduction in the Type II endoleak rate through active sac management. Type II endoleaks were only reported in 2 patients out of > 200 patients treated with ChEVAS in the 5 studies that were reviewed above (**Table 3**). Only 1 of these Type II endoleaks required interventional intervention.^{96,115} A recent systematic review of EVAS studies showed the rate of Type II endoleaks was 1.8%, a 30-days.¹²³ This compares well to a rate of 10.2% for Type II endoleaks at 30-days, that has been reported for EVAR, in a systematic review of 32 studies.¹²⁴

Another advantage of EVAS, which may also apply to ChEVAS is a reduction of radiation dose and procedural time compared to EVAR.¹²⁵ Also, systematic review of EVAS showed a 30-day mortality rate of 1.0% for elective patients and 2.6% including emergency cases.¹²³ These rates are comparable to EVAR, but lower than for open repair.¹²⁶

Finally, as Nellix utilizes active sac management in both EVAS and ChEVAS, it is expected that the potential mortality benefit may also be applicable to the ChEVAS procedure. Although many factors impact the long-term survival, underlying cardiovascular disease explains much of the risk associated with the high rate of adverse cardiovascular events. The relationship between inflammation and atherothrombosis has been established in the last decade. After an endograft excludes the aneurysm sac using EVAR, the aneurysm remains biologically active. The aneurysm sac undergoes a biological response related to a change in pressure and produces an inflammatory response in order to induce fibrosis and regression. If the aneurysm sac is not successfully excluded due to endoleaks, intraluminal thrombus, and pressure transmitted from a porous endograft, the inflammation does not subside and may accelerate. Consequently, the risk of cardiovascular events may increase due to the ongoing inflammatory response. However, EVAS utilizes active sac management to completely seal with the EndoBags and exclude the aneurysm sac. As a result, this seal may reduce the wall stress on the aneurysm sac and blunt the inflammatory response and cardiovascular risk.

Despite the potential risk associated with ChEVAS, it also offers distinct potential benefits over currently available standard treatments for complex AAA, including open surgical repair, fEVAR, and ChEVAR. As such, there is adequate justification to initiate a study to further evaluate the risks and benefits of ChEVAS.

3 OBJECTIVES AND ENDPOINTS

3.1 1-MONTH PRIMARY ENDPOINT

The primary 1-month endpoint is defined in terms of an event rate, and includes technical failure and any of the following:

- *Severe Bowel Ischemia* – lack of adequate blood flow to the intestines leading to surgical/endovascular intervention or death and reported within 30 days of the index procedure
- *Permanent Paraplegia/Paraparesis* – event reported within 30 days of the index procedure without resolution at 30 days post-procedure
- *Renal Failure* – new onset renal failure requiring dialysis that remains on-going at 30 days post-procedure
- *Disabling Stroke* – new neurological deficit resulting from vascular insult reported within 30 days of the index procedure without resolution at 6 months post-procedure. Disabling is considered a value of 2 (slight disability) or above on the modified Rankin Scale (mRS) at both the 1-month and 6-month visits.
- *Abdominal Aortic Aneurysm Rupture* - Intraoperative and Post-procedural rupture through the aneurysm wall within the stented segment of the aorta reported within 30 days of the index procedure.
- *Aneurysm-related mortality* - death reported within 30 days of the index endovascular procedure

The technical success component of the endpoint (counterpart to technical failure) is defined as:

- a. Successful access and delivery of all ChEVAS components (i.e., ability to deliver each component to the intended location, without the need for unanticipated corrective intervention related to delivery);
- b. Successful and accurate deployment, defined as:
 - i. Deployment of the Nellix stent-grafts, Ovation limbs, and chimney(s) in the planned location;
 - ii. Patency of the Nellix stent-grafts, Ovation limbs, and chimney(s) with absence of device deformations (e.g., kinks¹, mal-deployment², misaligned deployment³) requiring unplanned placement of an additional device within the endovascular stent-grafts or chimney(s);
 - iii. Adequate seal without the need for unanticipated corrective interventions⁴. No use of components outside the defined ChEVAS System for the purpose of achieving seal. The use of adjunctive stenting for purposes outside of achieving seal or use

¹ Defined as a focal narrowing of the stent lumen of >50%, with concurrent stent wall deformation at that location.

² Defined as concluding the procedure without having all components of the ChEVAS System successfully deployed.

³ Defined as, at the conclusion of the procedure, a > 10mm difference between the top of the Nellix stents, or the top of a visceral stent being > 14mm below the Nellix stent (the bag shelf is 4mm below the top of the Nellix stents).

⁴ Concomitant procedures, including those for infrequently encountered circumstances, may be anticipated and prepared for as part of a comprehensive endovascular approach

of adjunctive stents that are part of the defined system, does not result in technical failure.⁵

- c. Successful withdrawal (i.e., successful withdrawal of the delivery systems without the need for unanticipated corrective intervention related to withdrawal).

Multiple events occurring to a subject are considered a single subject failure for the purposes of calculating the composite one-month rate, as the rate is based on the total number of subjects. Since none of these variables are restricted by imaging requirements for detection, the cutoff date for the endpoint is exactly 30 days from the index procedure.

3.2 1-YEAR PRIMARY ENDPOINT

The primary 1-year endpoint is a blend of safety and effectiveness indicators. The endpoint is defined as the absence of:

- Abdominal aortic aneurysm rupture (0 - 365 days);
- Aneurysm-related mortality (0 – 365 days)
- Imaging-determined events at the 12-month imaging window. These do not require an intervention within 12 months to count as events:
 - Type I or Type III endoleak
 - Migration⁶ > 10mm
 - Sac Expansion⁷ > 5mm
 - Loss of Patency (100% occlusion) in Branches⁸, Nellix, or iliac limbs not seen at the index procedure
- Open conversion through day 365

⁵ Examples of acceptable procedures include:

- Placing an additional stent (Verta or Lifestent) to correct kink in visceral vessel (or a kink in the stent resulting from the vessel anatomy) or to smooth transition from Verta to visceral vessel (transition stenting)
- Placing an additional stent (Verta or Lifestent) to treat pre-existing visceral artery stenosis (spot stenting)
- Placing Verta stent within initial Verta stent due to length discrepancy, need to achieve a Verta length not covered by available lengths, or inadequate initial seal
- Placing Ovation limb to extend Nellix in order to obtain an adequate distal seal;
- Coiling of non-treated branch vessels
- Ballooning of any vessel or stent

⁶ As measured by the proximal end of the Nellix stents relative to the reference artery

⁷ As measured across the maximum transverse sac diameter relative to the 1-month scan

⁸ Branches refer to stents in the left renal artery, right renal artery, and superior mesenteric artery

- Other major device-related⁹ surgical or endovascular re-interventions through day 365 for:
 - Type I or III endoleak, or gutters
 - Migration
 - Thrombotic events/Occlusions - complete loss of patency in any of the components of the ChEVAS System due to thrombotic events and/or device deformation
 - Device deformation resulting from fracture, that leads to clinical sequelae of vessel stenosis progressing to decreased perfusion, or puncturing of graft material leading to endoleak
 - Relining of the Nellix Stents to correct stenosis or kink
 - Mal-deployed device that leads to clinical sequelae of migration, endoleak, or thrombosis
 - Device infection

Non-major interventions are not included in the endpoint:

- Endovascular intervention for branch stenosis (within the stent or distal to the stent) for a reason other than stent fracture
- Interventions for Type II endoleaks
- Non endovascular treatments for procedural complications that are non-device specific, e.g., seroma, surgical site infection etc.

The 1-year endpoint is a collection of variables that may be detected at any time or require imaging to be detected. As such, variables are evaluated differently for the “1-year” timeframe. Variables lacking imaging restrictions (rupture, mortality, interventions) are evaluated until day 365 for the 1-year endpoint as the exact day of the event will be known. Onset dates for imaging-driven variables are unknown (they have may occurred at any time prior to the imaging scan that detected them) and thus are evaluated at the one-year imaging window as determined by the scan date. Presence of positive imaging-related findings within the 1-month or 6-month imaging windows does not factor into the endpoint analysis. Rather, the endpoint analysis restricts positive findings to only those within the 1-year imaging window. Imaging results used in the endpoint analysis will be sourced from core lab assessments.

In contrast to classic EVAR studies that analyze safety at 1 month and effectiveness at 1 year, the ChEVAS study is designed to evaluate both safety and effectiveness across dual endpoints (thus, passing both endpoints will indicate the trial has demonstrated safety and effectiveness).

⁹ Device refers to main Nellix EndoVascular Aneurysm Sealing System (Nellix System), Verta Self-Expanding Stent Graft and Ovation iX iliac Limbs/Extensions

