1.3 SCHEDULE OF ACTIVITIES (SOA)

A schedule of activities is provided in Table 1 below, with further detail provided in Section 8.

TABLE 1 : SCHEDULE OF ACTIVITIES (SOA)

Procedures	Screening	Enrollment Day 0	Discharge Day 0 till discharge	30-Day Visit Day 30 +/- 14 days	6-Month Visit Day 180 +/-30 days	1-Year Visit Day 365 +/-60 days	2-Year Visit Day 730 +/-90 days	3-Year Visit Day 1095 +/-90 days	4-Year Visit Day 1460 +/-90 days	5-Year Visit Day 1825 +/-90 days
Informed consent	X									
Demographics	X									
Medical history	X									
Device Implantation		X								
Vitals (including height and weight)	X	X		X	X	X	X	X	X	X
Serum creatinine	X			X	X	X	X	X	X	X
Serum Pregnancy Test ^a	X									
CTA ^b	X			X	X	X	X	X	X	X
X-ray ^c				X		X		X		X
Complete Case Report Forms (CRFs)/Data collection	X	X	X	X	X	X	X	X	X	X
Adverse event review and evaluation		X	X	X	X	X	X	X	X	X

a: Only for women of childbearing potential

b: For follow-up (not screening), a non-contrast CT and duplex ultrasound may be done in place of the CTA, if the subject has renal insufficiency.

c: 2-view abdominal (left and right oblique)

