8.5.10 MAJOR ADVERSE EVENTS

Major Adverse Events (MAE) are defined as below and will be adjudicated by the Clinical Events Committee.

Major Adverse Event: An event occurring during the study that meets one of the following criteria:

- *All-Cause Death*: Any death occurring during the study period, regardless of cause. Death will be further categorized as one of the following:
 - *Aneurysm-related death* – any death occurring within 30 days from the date of the procedure, regardless of cause, and death due to aneurysm rupture or following any procedure intended to treat the aneurysm
 - *Cardiac-related death* – death due to arrhythmia, heart failure (including cardiogenic shock), or myocardial infarction
 - *Pulmonary-related death* – death due to pulmonary edema, respiratory failure, or pulmonary embolism
 - *Vascular-related death* – death due to stroke, cerebral hemorrhage, or other clear vascular event that is not categorized as cardiac-related, pulmonary-related or aneurysm-related
 - *Other* – a death that cannot be clearly categorized as above, but where information on the circumstances of death is available
 - *Unknown* – a death where no information is available
- *Bowel Ischemia*: The lack of adequate blood flow to the intestines that requires intensification of medical therapy or surgical/endovascular intervention
- *Paraplegia*: Paralysis of the lower extremities inclusive of the lower trunk, with deficits present at the subsequent scheduled follow-up visit
- *Renal Failure*: renal injury resulting in the need for temporary or permanent dialysis
- *Disabling Stroke*: new neurological deficit resulting from vascular insult confirmed by imaging. Disabling is considered a value of 2 (slight disability) or above on the modified Rankin Scale (mRS)

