9.2 SAMPLE SIZE DETERMINATION

The number of patients enrolled into this study is driven by the performance goals, expected device performance, and requirements for the alpha error and power. Due to the decrease in number of evaluable subjects at 1 year, the size of the study is determined entirely by the 1-year primary endpoint. Given a minimum power requirement of 80%, alpha=0.05, target goal=75%, estimated 1-year performance of 85.7%, and the univariate binomial test plan, a minimum evaluable sample size of 103 is needed. Accounting for an approximate drop-out rate of 14%, 120 subjects would be needed to achieve the minimum power and alpha requirements. The 1-month endpoint assumes a target goal of 25%, estimated performance of 14.5%, and a similar univariate binomial test structure. Given that all 120 subjects will be analyzed for the primary 1-month endpoint, the 1-month endpoint has power of 85.6%. This is described further in the SAP.

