9.4.2 ANALYSIS OF THE PRIMARY ENDPOINT(S)

The components that go into the endpoints and the methodology of their analysis are detailed thoroughly in the SAP.

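### The 1-month stroke component requires mRS of 2 or more at both the 1-month and 6-month visits, so, read literally, a stroke subject alive at day 30 who dies before the 6-month score is a non-event

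*Combined protocol and SAP*

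**What the plan says.** Protocol §3.1 defines the 1-month primary endpoint as technical failure or any of six clinical events. The stroke component needs a new deficit of vascular origin, reported within 30 days and still unresolved at 6 months, and adds: "Disabling is considered a value of 2 (slight disability) or above on the modified Rankin Scale (mRS) at both the 1-month and 6-month visits". The death component covers deaths within 30 days of the index procedure only.

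Two other statements bear on timing. The section closes by saying that "the cutoff date for the endpoint is exactly 30 days from the index procedure". Permanent paraplegia or paraparesis, in the same list, is judged at day 30: "event reported within 30 days of the index procedure without resolution at 30 days post-procedure". Renal failure is likewise judged at day 30.

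On the denominator, §9.2 says: "Given that all 120 subjects will be analyzed for the primary 1-month endpoint". On collection, §8.4 calls for an mRS examination when a neurological change is suspected. Table 1 has no mRS row. It gives the first follow-up visit as "30-Day Visit Day 30 +/- 14 days" and the 6-month visit as day 180 ± 30.

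On method, §9.4.2 defers: "The components that go into the endpoints and the methodology of their analysis are detailed thoroughly in the SAP". The text of that SAP is not in the file reviewed.

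**The concern.** A component meant to capture the worst neurological outcome should not score death more favourably than survival with disability. As worded it can. The subject must live to the 6-month visit and be scored there before the stroke counts, and the endpoint's death component has closed by then. Withdrawal, loss to follow-up or an unrecorded score also leaves the definition unmet, while the subject stays in the denominator of 120.

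This matters for this technique because §2.4.1 names stroke from upper-extremity access as a specific risk. The 1-month endpoint is one of two that must both be passed, and stroke is not a component of the 1-year endpoint in §3.2. The event would still be reported descriptively as a major adverse event, since the stroke definition in §8.5.10 has no two-visit condition, but it could be missing from the tested 1-month result.

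**Working it through.** **Step 1: apply the wording to cases.** Each subject has a disabling stroke reported by day 30 and meets no other component.

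| Course after the stroke | Stroke component | Death component | 1-month result |
|---|---|---|---|
| Dies by day 30 | not needed | met | event |
| Alive, mRS 2 or more at both visits, unresolved at 6 months | met | not met | event |
| Dies between day 31 and the 6-month mRS | not met (no 6-month score) | not met (after day 30) | non-event |
| Alive, mRS missing at either visit | not met | not met | non-event |

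The 6-month window is 180 − 30 = day 150 to 180 + 30 = day 210, so the gap in the third row can run from day 31 to as late as day 210. No text in the file scores death as a disabling mRS, imputes a missing score or substitutes another one.

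**Step 2: reproduce the plan's power.** Inputs from §9.1 and §9.2: n = 120, goal 25%, expected rate 14.5%, alpha 0.05, exact binomial test, directional alternative. Let X be the number of counted events.

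- The pass limit is the largest c with P(X ≤ c | 120, 0.25) ≤ 0.05.
- P(X ≤ 21 | 120, 0.25) = 0.0330 and P(X ≤ 22 | 120, 0.25) = 0.0534, so c = 21.
- Power = P(X ≤ 21 | 120, 0.145) = 0.856, which matches the stated 85.6%.

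§9.2 does not say whether alpha is one-sided. One-sided 0.05 reproduces the figure. One-sided 0.025 gives c = 20 and power 0.792, which does not.

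**Step 3: effect of uncounted strokes (the counts are assumed).** If exactly k true events go uncounted, the trial passes with up to 21 + k true events. At a true rate of 25%, P(pass) = P(X ≤ 21 + k | 120, 0.25):

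| k | Limit on true events | P(pass) |
|---|---|---|
| 0 | 21 | 3.3% |
| 1 | 22 | 5.3% |
| 2 | 23 | 8.3% |
| 3 | 24 | 12.2% |

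These are error rates only if the 25% goal was set for an endpoint that includes such strokes. The documents do not say.

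**Step 4: is k of 1 to 3 plausible?** The text below Table 3 gives stroke of any severity as 2.6% to 7.1%, that is 0.026 × 120 = 3.1 to 0.071 × 120 = 8.5 strokes. Suppose the 14% one-year drop-out allowance of §9.2 also described loss of the mRS (an assumption; stroke patients may die or drop out more often). Then 0.14 × 3.1 = 0.4 to 0.14 × 8.5 = 1.2 would be uncounted, before removing non-disabling strokes and subjects who fail for another reason. Zero or one is therefore the likely order on this assumption. Two or three would need heavier loss among stroke subjects.

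**The case against.** **The missing outcome is unlikely, and the SAP may cover it.** §8.4 triggers an mRS, §10.1.5 follows events to resolution or stabilization, and the CEC reviews all deaths and potential major adverse events. This stands as mitigation. These provisions make a missing score less likely, but none says how the subject is counted, and a death before 6 months cannot be prevented by better collection. The SAP may hold the rule, so the fix is conditional on that.

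**The cutoff sentence is loose wording.** §3.1 already separates onset (by day 30) from persistence (6 months), and the sentence explains why no imaging window is needed. That is a fair reading, and a longer confirmation period for stroke than for paraplegia is a legitimate choice. The two statements still do not agree as written.

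**Stronger readings that the documents do not support.**

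- A reader might infer that a stroke death after day 30 escapes both primary endpoints. §8.5.10 does have a vascular category, "death due to stroke, cerebral hemorrhage, or other clear vascular event that is not categorized as cardiac-related, pulmonary-related or aneurysm-related", but that category yields to an aneurysm-related classification. The same section includes as aneurysm-related "death due to aneurysm rupture or following any procedure intended to treat the aneurysm", which, read literally, could include the index repair. §8.5.11 also lets the CEC class a death as aneurysm-related. So there are routes into the 1-year endpoint, although no rule ensures that one is taken.
- A reader might infer that the two descriptions of aneurysm-related death put the 1-year count in doubt. §8.5.11 introduces its definitions as those captured for endpoint analysis, whereas §8.5.10 sorts deaths for a listing that §9.4.4 treats descriptively. That largely answers the question, and it is not part of this point.
- A reader might infer that a stroke on days 17 to 30, after an early visit in a window opening on day 16, has no post-stroke 1-month score. It may lack one, but an mRS done under §8.4 by day 44 would fall inside the window.

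**Conclusion.** The point holds in a limited form. As worded, §3.1 gives the wrong 1-month result for one kind of subject: a disabling stroke by day 30, survival past day 30, and death before the 6-month mRS. It also leaves subjects with a missing score uncounted. This follows from the stated rule and does not depend on the arithmetic.

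The numerical effect is illustrative. It rests on an assumed number of uncounted strokes and on how the 25% goal was set. A reader might infer that the 1-month test has an inflated type I error. That follows only if the goal was meant to include these strokes; if it was set for the endpoint exactly as worded, there is no inflation. The number affected is probably small, but with a limit of 21 of 120 a single subject can decide the result. The change should be made unless the SAP already makes it. Confidence is moderate because the SAP was not available.

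**What to change.** Unless the SAP already does this:

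1. In §3.1, state that day 30 governs stroke onset and that disability is confirmed at 6 months, and reconcile this with the sentence on the 30-day cutoff.
2. Count a stroke with onset by day 30 followed by death before the 6-month mRS as an event, unless resolution or an mRS below 2 was documented after the stroke.
3. Where mRS is missing for another reason, use the last post-stroke mRS or CEC adjudication, and add a sensitivity analysis that counts cases still unresolved as events. Other conventions are possible; what matters is that one is fixed in advance.
4. List mRS at the 1-month and 6-month visits in Table 1 for subjects with a stroke, taken after onset, in line with §8.4.

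The cost is wording in the protocol, SAP and CEC charter, plus scheduled mRS for the few subjects with a stroke. A few more events may count, which could lower 1-month power below 85.6%. If the 14.5% planning rate leaves such strokes out (not stated), exactly one more counted event gives P(X ≤ 20 | 120, 0.145) = 79.2%, and exactly two give P(X ≤ 19 | 120, 0.145) = 71.4%. If the planning rate already includes them, planned power is unchanged.
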